7.2.6 Adverse events

All information obtained on adverse events will be listed by treatment and subject.

Summary tables for adverse events (AEs) will summarize only on-treatment events, with a start date during the on-treatment period (treatment-emergent AEs).

The number and percentage of subjects with adverse events will be tabulated by body system and preferred term with a breakdown by treatment. Separate summaries will be provided for study medication related adverse events and other significant adverse events leading to discontinuation.

The number of deaths resulting from SAEs suspected to be related to study treatment and SAEs irrespective of study treatment relationship will be provided by SOC and PT until day 29 and after day 29.

The number of deaths resulting from SAEs suspected to be related to study treatment and SAEs irrespective of study treatment relationship will be provided by PT until day 29 and after day 29.

A subject with multiple adverse events within a body system is only counted once towards the total of this body system and treatment.

For the legal requirements of ClinicalTrials.gov and EudraCT, two tables are required:

on treatment emergent adverse events which are not serious adverse events and on treatment emergent serious adverse events and SAE suspected to be related to study treatment will be provided by system organ class and preferred term on the safety analysis set.

If for a same patient, several consecutive AEs (irrespective of study treatment causality, seriousness and severity) occurred with the same SOC and PT:

- a single occurrence will be counted if there is ≤ 1 day gap between the end date of the preceding AE and the start date of the consecutive AE
- more than one occurrence will be counted if there is > 1 day gap between the end date of the preceding AE and the start date of the consecutive AE.

For occurrence, the presence of at least one SAE / SAE suspected to be related to study treatment / non SAE has to be checked in a block e.g., among AE's in a ≤ 1 day gap block, if at least one SAE is occurring, then one occurrence is calculated for that SAE.

The SAEs and deaths by State will be graphically presented in a barchart. Refer to [Section 10.8](#) for details on the state.

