10.1 Definition of adverse events and reporting requirements

10.1.1 Adverse events

An adverse event (AE) is any untoward medical occurrence (e.g. any unfavorable and unintended sign [including abnormal laboratory findings], symptom or disease) in a clinical investigation participant after providing written informed consent for participation in the study. Therefore, an AE may or may not be temporally or causally associated with the use of a medicinal (investigational) product.

The investigator has the responsibility for managing the safety of individual participant and identifying adverse events.

Novartis qualified medical personnel will be readily available to advise on trial related medical questions or problems.

The occurrence of adverse events must be sought by non-directive questioning of the participant at each visit during the study. Adverse events also may be detected when they are volunteered by the participant during or between visits or through physical examination findings, laboratory test findings, or other assessments.

Adverse events must be recorded under the signs, symptoms, or diagnosis associated with them, accompanied by the following information (as far as possible) (if the event is serious refer to [Section 10.1.2](#)):

1. Severity grade:

- mild: usually transient in nature and generally not interfering with normal activities
- moderate: sufficiently discomforting to interfere with normal activities
- severe: prevents normal activities

2. Its relationship to the study treatment. If the event is due to lack of efficacy or progression of underlying illness (i.e. progression of the study indication) the assessment of causality will usually be 'Not suspected.' The rationale for this guidance is that the symptoms of a lack of efficacy or progression of underlying illness are not caused by the trial drug, they happen in spite of its administration and/or both lack of efficacy and progression of underlying disease can only be evaluated meaningfully by an analysis of cohorts, not on a single participant
3. Its duration (start and end dates) or if the event is ongoing, an outcome of not recovered/not resolved must be reported
4. Whether it constitutes a SAE (see [Section 10.1.2](#) for definition of SAE) and which seriousness criteria have been met
5. Action taken regarding with study treatment.

All adverse events must be treated appropriately. Treatment may include one or more of the following:

1. Dose not changed

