2. Dose Reduced/increased
3. Drug interrupted/withdrawn

6. Its outcome (i.e., recovery status or whether it was fatal)

Conditions that were already present at the time of informed consent should be recorded in medical history of the participant.

Adverse events (including lab abnormalities that constitute AEs) should be described using a diagnosis whenever possible, rather than individual underlying signs and symptoms.

Adverse event monitoring should be continued until the end of study.

Once an adverse event is detected, it must be followed until its resolution or until it is judged to be permanent (e.g., continuing at the end of the study), and assessment must be made at each visit (or more frequently, if necessary) of any changes in severity, the suspected relationship to the interventions required to treat it, and the outcome.

Information about adverse drug reactions for the investigational drug can be found in the IB.

Abnormal laboratory values or test results constitute AEs only if they fulfill at least one of the following criteria:

- 1) they induce clinical signs or symptoms
- 2) they are considered clinically significant
- 3) they require therapy

Clinically significant abnormal laboratory values or test results must be identified through a review of values outside of normal ranges/clinically notable ranges, significant changes from baseline or the previous visit, or values which are considered to be non-typical in participant with the underlying disease.

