12.5.2 Safety endpoints

For all safety analyses, the safety set will be used. All listings and tables will be presented by treatment group.

Safety summaries (tables, figures) include only data from the on-treatment period with the exception of baseline data which will also be summarized where appropriate (e.g. change from baseline summaries). In addition, a separate summary for death including on treatment and post treatment deaths will be provided. In particular, summary tables for adverse events (AEs) will summarize only on-treatment events, with a start date during the on-treatment period (treatment-emergent AEs).

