12.5.2.1 Adverse events

All information obtained on adverse events will be displayed by treatment group and participant.

The number (and percentage) of participants with treatment emergent adverse events (events started after the first dose of study medication or events present prior to start of randomized treatment but increased in severity based on preferred term) will be summarized in the following ways:

- by treatment, primary system organ class and preferred term.
- by treatment, primary system organ class, preferred term and maximum severity.

Separate summaries will be provided for study medication related adverse events, death, serious adverse events and other significant adverse events leading to discontinuation.

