1.1 Scope of document

The RAP documents contain detailed information to aid the production of Statistics & Programming input into the Clinical Study Report (CSR) for trial “**CMAS825F12201**”.

The Statistical analysis plan (SAP) describes the implementation of the statistical analysis planned in the protocol to be reported in the CSR as well as any potential IA. The data presentation and analyses for the DMC are not part of this analysis plan.

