7.2 Descriptive analyses

Safety summaries (tables, figures) include only data from the on-treatment period with the exception of baseline data, which will also be summarized where appropriate (e.g. change from baseline summaries).

The on-treatment period lasts from the date of administration of study treatment to Day 127.

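### The protocol holds two conflicting definitions of a treatment-emergent adverse event, and the SAP silently adopts the narrower one, so some post-dose worsening can drop out of the AE tables

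*SAP*

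**What the plan says.** Protocol 12.5.2.1 has two classes of treatment-emergent event: those that begin after the first dose, and "events present prior to start of randomized treatment but increased in severity based on preferred term".

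The parent section, Protocol 12.5.2, restricts the AE summary tables to events "with a start date during the on-treatment period (treatment-emergent AEs". SAP 7.2.6 repeats that sentence, so its tables "will summarize only on-treatment events, with a start date during the on-treatment period". SAP 7.2 sets the window: "The on-treatment period lasts from the date of administration of study treatment to Day 127". Neither SAP section mentions worsening. SAP 1.1 says that the SAP "describes the implementation of the statistical analysis planned in the protocol".

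On data collection, Protocol 10.1.1 defines an AE as an occurrence "in a clinical investigation participant after providing written informed consent for participation in the study". It adds: "Conditions that were already present at the time of informed consent should be recorded in medical history of the participant".

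**The concern.** The two definitions disagree about an AE that is already present at dosing and then gets worse. The broader rule counts it as treatment-emergent. The narrower rule looks only at the onset date and leaves it out, even if the later course is serious.

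The same flag feeds the AE tables, the SAE tables and the two tables that SAP 7.2.6 plans for the public registries. The rule applies equally to both arms, so it does not create a difference between them. But the events it can remove are those that deteriorated after the infusion, which is one place where harm from the drug could show. AE collection starts at consent, before dosing, so such events are possible in this design.

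**Working it through.** No arithmetic applies. The check sets the rules side by side and runs each type of event through both.

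**Rule A** (Protocol 12.5.2.1): onset after the first dose, or onset before it with an increase in severity for the same preferred term.

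**Rule B** (Protocol 12.5.2 and SAP 7.2.6, with the SAP 7.2 window): onset date from the calendar date of dosing to Day 127.

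| Event | Rule A | Rule B |
|---|---|---|
| 1. Starts after the infusion, by Day 127 | counted | counted |
| 2. Starts on the dosing date before the infusion, then worsens | counted | counted |
| 3. Starts on the dosing date before the infusion, never worsens | not counted | counted |
| 4. Starts after consent on an earlier date, never worsens | not counted | not counted |
| 5. Starts after consent on an earlier date, worsens after the infusion, new record opened | counted | counted |
| 6. As 5, but kept on the existing record | counted | **not counted** |
| 7. Present at consent, worsens after the infusion and is entered as an AE dated then | counted | counted |

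The rules part company in two rows. In row 6, Rule B loses an event. In row 3, it includes one that Rule A would not, because SAP 7.2 works in dates rather than times.

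**Row 7.** A condition present at consent belongs in medical history. Protocol 8.2.1 requires significant later findings that meet the AE definition to be entered as AEs, and the SAE definition in Protocol 10.1.2 covers worsening of a pre-existing condition. Deterioration of the presenting illness after the infusion can therefore enter with a post-dose date and be counted under either rule.

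**Row 5 or row 6?** The documents do not say whether a severity increase opens a new record.
- Protocol 10.1.1 has each AE followed to resolution, with changes in severity assessed at every visit. That reads like one continuing record.
- Protocol 10.1.3 has progression of an SAE reported as follow-up to the first episode. That is a safety-reporting rule rather than a CRF rule, but it points the same way.
- SAP 7.2.6 has a rule for consecutive AEs with the same preferred term whatever their severity, which suggests that split records can occur.

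Whether an event is tabulated would then depend on site practice that no visible text fixes.

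**How wide is row 6?** The screening, baseline and treatment visit lasts at most 24 hours (Protocol 3), and treatment may begin as soon as eligibility is confirmed (Table 8-1, footnote 2). Four things must coincide: consent on an earlier calendar date than dosing, AE onset before that date ends, worsening after the infusion, and no new record.

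**What survives.** SAP 7.2.6 lists all AE information. Protocol 12.5.2 plans a death summary covering on-treatment and post-treatment deaths. The loss is confined to the summary tables.

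**The case against.** The strongest reply is that the SAP does what the protocol tells it: its sentence is that of Protocol 12.5.2. The exposed window is short, worsening of conditions present at consent has its own route into the AE data, nothing vanishes from the listings, deaths are summarised separately, and the DMC reviews mortality and SAEs (Protocol 9.1.4). On that view this is an editorial mismatch.

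Most of this stands as to size. It does not remove the contradiction, since a programmer cannot satisfy both 12.5.2 and 12.5.2.1.

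Several stronger readings are tempting, and the documents do not support them:
- A reader might infer that the SAP alone discards a protocol class. The narrower rule is already in the protocol; what the SAP does is settle the conflict without saying so.
- A reader might infer that only events after the infusion are counted, or that all worsening of pre-dose events is missing. Rows 2, 5 and 7 show otherwise.
- A reader might assume that a few per cent of the 120 participants are affected. No section gives a rate of AEs between consent and dosing, so any such count would be invented.
- A reader might cite the likelihood of deterioration soon after admission (Protocol 4.1) as evidence that the window contains many events. The protocol uses it to justify rapid entry, which shortens the window.

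One objection bears on the remedy. Protocol 10.1.1 asks for AE start and end dates, not times, so ordering same-day events by infusion time cannot be assumed feasible.

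**Conclusion.** The conflict is real and lies first within the protocol, between 12.5.2 and 12.5.2.1; SAP 7.2.6 carries the narrower rule forward. Its consequence is limited. An AE with onset after consent, on a calendar date before dosing, that worsens after the infusion and stays on its existing record can be missing from the AE, SAE and registry summary tables.

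The size cannot be estimated from the documents. It is probably small, because of the 24-hour limit and the calendar-date start, and it is zero if sites always open a new record on worsening. The conclusion assumes that the visible text is the whole rule and that no CRF completion guideline settles the recording question. The point is minor and concerns safety reporting only; the primary analysis is unaffected.

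**What to change.** Use the definition of Protocol 12.5.2.1 in Protocol 12.5.2 and SAP 7.2.6. An AE is treatment-emergent if it starts on or after dosing, or if it starts earlier and its severity for the same preferred term increases after dosing.

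State how that increase is captured, either as a dated severity change on the existing record or as a new record dated at the worsening. Without this the second class cannot be programmed: Protocol 10.1.1 requires severity changes to be assessed but does not say that they are stored with dates.

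Use infusion time to order same-day events only if AE onset time is collected. Otherwise keep the calendar-date rule and say that a same-day pre-infusion event will be counted.

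The cost is one or two sentences in each document, a CRF completion instruction and minor programming. If severity changes have not been dated so far, the instruction asks sites for something new.

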7.2.7 Graphical presentation

For all vital signs, ECGs and laboratory parameters the following graphical presentations will be provided:

Panels of individual spaghetti plots over time for each parameter and their change from baseline will be drawn. The profiles of all participants in the respective treatment group will be included in these graphs as grey lines in the background and the respective individual participants profile will be plotted with darker color in the foreground. The respective applicable normal ranges will be added and it will be indicated by a symbol if a patient died.

Means (+/- SE) will be plotted over time by treatment group

Commercially Confidential Information

Commercially Confidential Information

Commercially Confidential Information

9 Reference list

10 Appendix

10.1 Units and conversions

Special care must be taken with respect to converting lab parameters prior to applying the scoring described below to avoid propagation of rounding errors. The following principles will be applied:

- If the unit of the original lab assessment from the local lab is equal to the unit used in the scoring table, this original value is used.
- In case the SI unit which is available within the SDTM data sets is equal to the unit used in the scoring table, the value converted to SI units is used.

- If neither the original nor the SI unit are matching the unit used in the scoring table then convert the original value from the local lab to the unit required by the scoring table. Note that for some parameters there are scoring tables available for different units.
- Do convert the value in SI units further.
- Do apply rounding to the precision required in the scoring table only after conversion to the unit used in the scoring table has been done.

10.1.1 Conversion for absolute neutrophil counts

If not reported the absolute neutrophil counts can be derived if

- % of neutrophils
- Total WBC

is available via the following formula:

$$\text{absolute neutrophil count} = \text{total WBC} * \text{neutrophil percentage}.$$

10.2 APACHE II

The APACHE II score is derived from a number of different clinical endpoints according to the scoring table as outlined in ([Knaus et al., 1985](#)):

1. Body temperature (°C)

Depending on the collection method selected apply the following correction factors before scoring:

- Core: no correction needed
- Axillary: + 1.0 °C
- Oral: + 0.5 °C
- No method selected: no correction.

2. Mean Arterial Pressure (mmHg)

In case the “method” is reported as “calculated” confirm the calculation by applying the following formula: $\text{MAP} = [\text{SBP} + (2 \times \text{DBP})] / 3$. If the reported and recalculated numbers differ by more than 10% use the recalculated value (i.e. if reported value < 0.9* recalculated value or reported value > 1.1* recalculated value)

3. Heart Rate (beats per minute)

If the participant has a pacemaker any HR ≤ 109 bpm will be scored to 0.

4. Respiratory Rate (breaths per minute)

5. Oxygenation: depending on the Fraction of inspired Oxygen (FiO2, where FiO2 is a value between 0 and 1 (i.e. not on % scale)):

- a. If $\text{FiO}_2 < 0.5$: use PaO_2 (mmHg)

- b. If $\text{FiO}_2 \geq 0.5$: use A-aDO_2 (mmHg): where A-aDO_2 is calculated as $\text{A-aDO}_2 = (\text{FiO}_2 \times 713 - \text{PaCO}_2/0.8) - \text{PaO}_2$

In case PaO2 is not available for a certain visit it can be derived from SPO2 if available instead using the following conversion table:

Table 10-1Conversion of SpO2 to PaO2

SpO2 (%)	PaO2 (mmHg)
80	44
81	45
82	46
83	47
84	49
85	50
86	52
87	53
88	55
89	57
90	60
91	62
92	65
93	69
94	73
95	79
96	86
97	96
98	112
99	145

In case PaCO2 is not available for a certain visit it can be derived from HCO3 if available instead using the following conversion:

$$\text{PaCO2 (mmHg)} = \text{HCO3(mEq/L)} * 1.5 + 8$$

6. Arterial pH: if Arterial pH is not available use Serum HCO3 (venous mMol/L) instead
7. Serum Sodium (mmol/L)
8. Serum Potassium (mmol/L)
9. Serum Creatinine (mg/dL=mg/100mL)
10. Hematocrit (%)

11. White Blood Count ($10^9/\text{L} = 1000/\text{mm}^3 = 10^3/\text{mm}^3$)

12. Age at screening (years)

13. Chronic Health Points at Screening:

Points are assigned only if for this patient “Did the subject experience Severe organ system insufficiency or is immunocompromised ?” is selected as “yes”.

- If “Did the subject experience Severe organ system insufficiency or is immunocompromised ?” = “no”, no points are assigned and a record should not be created for this question in the SDTM data set.
- If “Did the subject experience Severe organ system insufficiency or is immunocompromised ?” is selected as “yes” Chronic Health points will be derived from “Admission Classification”:
 - Medical(non-operative)
 - Emergency post-operative
 - Elective post-operative

If in this scenario none of these conditions is selected the Chronic Health points will be set to 0.

14. Glasgow Coma Score: First each sub-score is scored according to the scoring table below

- Best Eye Response
- Motor Response
- Verbal Response

Then these three subscores are added up to obtain the scoring of the “Total Glasgow Coma Score”. The value included in the APACHE II for Glasgow-Coma-Score is then = 15 – “Total Glasgow Coma Score”.

SDTM Mapping strategy

APACHE II specific mapping strategy: It provides guidance on how the result variables (RSORRES, RSSTRESC, and RSSTRESN) should be populated for the measure. All original results are represented with preferred terminology in RSORRES. This result is then transformed into a standard numeric score in RSSTRESN and a character representation of the standard numeric score in RSSTRESC.

To obtain the total APACHE II score all 14 derived values of RSSTRESN are then added up. If one item is missing the APACHE II score at SDTM level for this visit is missing. Missing data imputation will be implemented at ADAM level.

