5.1 Inclusion criteria

Participants eligible for inclusion in this study must meet **all** of the following criteria:

1. Male and female patients aged ≥ 18 years at screening
2. Signed Informed Consent Form (ICF) by patient capable of giving consent, or, when the patient is not capable of giving consent, by his or her legal/authorized representative (if allowed according to local requirements)
3. Clinically diagnosed with the SARS-CoV-2 virus by polymerase chain reaction (PCR) or by other approved diagnostic methodology within 7 days prior to randomization

4. Hospitalized with COVID-19-induced pneumonia evidenced by chest x-ray, computed tomography scan (CT scan) or magnetic resonance scan (MR scan) (taken within 5 days prior to randomization)
5. Impaired respiratory function, defined as peripheral oxygen saturation (SpO_2) $\leq 93\%$ on room air or partial pressure of oxygen (PaO_2) / fraction of inspired oxygen (FiO_2) <300 millimeter of mercury (mmHg) at time of screening For cities located at altitudes greater than 2500 m above sea level, these will be substituted with $\text{SpO}_2 <90\%$ and $\text{PaO}_2/\text{FiO}_2 <250$ mmHg
6. Acute Physiologic Assessment and Chronic Health Evaluation (APACHE) II score of ≥ 10 at time of screening
7. CRP ≥ 20 mg/L or ferritin level ≥ 600 $\mu\text{g}/\text{L}$ at screening
8. Body weight between 45 kg and 145 kg, inclusive, at screening
9. Ability to comply with the study protocol, in the investigator's judgment

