16.4 Appendix 4: ICU scores

Table 16-3 APACHE II

	Variable	Unit
	Age	years
	Glasgow Coma Score	
Vitals	Body temperature	°C
	Mean arterial pressure (MAP)	mmHg
	Heart rate	bpm
	Respiratory rate	breaths/m
Oxygenation	FiO ₂	%
	PaO ₂	mmHg
	Arterial pH	
	PaCO ₂	mmHg
	Altitude of site	Meters above sea level
Chemistry	Sodium	mEq/L
	Potassium	mEq/L
	Creatinine	mg/dL
	Acute Renal Failure	Yes/No
Hematology	Hematocrit	%
	White blood cell (WBC) count	×10 ⁹ /L
	Severe organ system insufficiency or is immunocompromised	Yes/No

Source: (Knaus et al 1985)

Table 16-4 Estimating PaO₂ from a given SpO₂

SpO ₂ (%)	PaO ₂ (mmHg)
80	44
81	45
82	46
83	47
84	49
85	50
86	52
87	53
88	55
89	57
90	60
91	62
92	65
93	69
94	73
95	79
96	86
97	96
98	112
99	145

Source : ([Vincent et al 2009](#))

Table 16-5 Estimating FiO₂

Method	O ₂ flow (l/min)	Estimated FiO ₂ (%) [*]
Nasal cannula	1	24
	2	28
	3	32
	4	36
	5	40
	6	44
Nasopharyngeal catheter	4	40
	5	50
	6	60
Face mask	5	40
	6-7	50
	7-8	60
Face mask with reservoir	6	60
	7	70
	8	80
	9	90
	10	95

Source : ([Vincent et al 2009](#))

* If patient is breathing air then estimated FiO₂ is 21%

Commercially Confidential Information

Table 16-8 GLASGOW COMA SCORE

Eye Opening

Criterion	Rating	Score
Open before stimulus	Spontaneous	4
After spoken or shouted request	To sound	3
After finger tip stimulus	To pressure	2
No opening at any time, no interfering factor	None	1
Closed by local factor	Non testable	NT

Verbal Response

Criterion	Rating	Score
Correctly gives name, place and date	Orientated	5
Not orientated but communication coherently	Confused	4
Intelligible single words	Words	3
Only moans/groans	Sounds	2
No audible response, no interfering factor	None	1
Factor interfering with communication	Non testable	NT

Best motor response

Criterion	Rating	Score
Obey 2-part request	Obeys commands	6
Brings hand above clavicle to stimulus on head/neck	Localising	5
Bends arm at elbow rapidly, but features not predominantly abnormal	Normal flexion	4
Bends arm at elbow, features clearly predominantly abnormal	Abnormal flexion	3
Extends arm at elbow	Extension	2
No movement in arms/legs, no interfering factor	None	1
Paralysed or other limiting factor	Non testable	NT

Source: (Teasdale and Jennett 1974)

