10.2.1 APACHE II Scoring

Temperature (°C)

RSORRES	RSSTRESC	RSSTRESN
>=41	4	4
39-40.9	3	3
38.5-38.9	1	1
36-38.4	0	0
34-35.9	1	1
32-33.9	2	2
30-31.9	3	3
≤29.9	4	4

Mean Arterial Pressure (mmHg)

RSORRES	RSSTRESC	RSSTRESN
>=160	4	4
130-159	3	3
110-129	2	2
70-109	0	0
50-69	2	2
≤49	4	4

Heart rate (BEATS/MIN)

Does the participant have a pacemaker?	RSORRES	RSSTRESC	RSSTRESN
Irrespective	>=180	4	4
Irrespective	140-179	3	3
Irrespective	110-139	2	2
No/unknown	70-109	0	0
No/unknown	55-69	2	2
No/unknown	40-54	3	3
No/unknown	≤39	4	4
Yes	≤109	0	0

Respiratory rate (BREATHS/MIN)

Note: Ventilated or non-ventilated patient scores will be the same as per table below

RSORRES	RSSTRESC	RSSTRESN
>=50	4	4
35-49	3	3
25-34	1	1
12-24	0	0
10-11	1	1

6-9	2	2
<=5	4	4

Impute the unit for respiratory rate as breaths/min in case it is missing.Oxygenation:

- If $\text{FiO}_2 \geq 0.5$ then use A-aDO₂ (mmHg)

RSORRES	RSSTRESC	RSSTRESN
>=500	4	4
350-499	3	3
200-349	2	2
<200	0	0

- If $\text{FiO}_2 < 0.5$ then use PaO₂ (mmHg)

RSORRES	RSSTRESC	RSSTRESN
>70	0	0
61-70	1	1
55-60	3	3
<55	4	4

If any value for <X, impute the value X in that case.

Arterial pH

- Use arterial pH if reported

RSORRES	RSSTRESC	RSSTRESN
>=7.7	4	4
7.6-7.69	3	3
7.5-7.59	1	1
7.33-7.49	0	0
7.25-7.32	2	2
7.15-7.24	3	3
<7.15	4	4

- Alternatively use Serum HCO₃ (mmol/L)

RSORRES	RSSTRESC	RSSTRESN
>=52	4	4
41-51.9	3	3
32-40.9	1	1
22-31.9	0	0
18-21.9	2	2
15-17.9	3	3
<15	4	4

Serum sodium (mmol/L)

RSORRES	RSSTRESC	RSSTRESN
>=180	4	4
160-179	3	3
155-159	2	2
150-154	1	1
130-149	0	0
120-129	2	2
111-119	3	3
<=110	4	4

Serum potassium (mmol/L)

RSORRES	RSSTRESC	RSSTRESN
>=7	4	4
6-6.9	3	3
5.5-5.9	1	1
3.5-5.4	0	0
3-3.4	1	1
2.5-2.9	2	2
<2.5	4	4

Serum creatinine (mg/dL)

RSORRES	RSSTRESC	RSSTRESN
>=3.5 and acute renal failure ="yes"	8	8
2-3.4 and acute renal failure ="yes"	6	6
1.5-1.9 and acute renal failure="yes"	4	4
0.6-1.4 and acute renal failure ="yes"	0	0
<0.6 and acute renal failure ="yes"	4	4
>=3.5	4	4
2-3.4	3	3
1.5-1.9	2	2
0.6-1.4	0	0
<0.6	2	2

Hematocrit (%)

RSORRES	RSSTRESC	RSSTRESN
>=60	4	4
50-59.9	2	2

46-49.9	1	1
30-45.9	0	0
20-29.9	2	2
<20	4	4

White Blood Count ($10^9/L$)

RSORRES	RSSTRESC	RSSTRESN
≥ 40	4	4
20-39.9	2	2
15-19.9	1	1
3-14.9	0	0
1-2.9	2	2
<1	4	4

Age points (years)

RSORRES	RSSTRESC	RSSTRESN
≤ 44	0	0
45-54	2	2
55-64	3	3
65-74	5	5
≥ 75	6	6

Chronic health points

RSORRES	RSSTRESC	RSSTRESN
For non-operative or emergency post-operative patients	5	5
For elective post-operative patients	2	2

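### For FiO2 of 0.5 or more, the SAP scores APACHE II oxygenation with a fixed sea-level constant, although site altitude is an APACHE II variable and sites above 2500 m are foreseen

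*SAP*

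**What the plan says.** SAP 10.2, item 5, sets the rule: "Oxygenation: depending on the Fraction of inspired Oxygen (FiO2, where FiO2 is a value between 0 and 1". Below 0.5, PaO2 is scored directly. At 0.5 or above, A-aDO2 is FiO2 x 713, minus PaCO2/0.8, minus PaO2. SAP 10.2.1 scores A-aDO2 below 200 mmHg as 0 points, 200-349 as 2, 350-499 as 3, and 500 or more as 4. Item 5 is shown in full and uses no altitude.

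Protocol Appendix 4, Table 16-3, lists "Altitude of site", in metres, in the oxygenation group of APACHE II variables. Inclusion criterion 5 in Protocol 5.1 adapts the SpO2 and PaO2/FiO2 limits: "For cities located at altitudes greater than 2500 m above sea level, these will be substituted with" lower values.

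If PaO2 is missing, SAP 10.2 says "it can be derived from SPO2 if available instead using the following conversion table". That table (Table 10-1) runs from SpO2 80% to 99% only.

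**The concern.** The protocol names altitude as an input to this score, and the derivation leaves it out. Because 713 is the sea-level value, at altitude the formula assumes more alveolar oxygen than is present. A-aDO2 comes out too large and the item is scored too high, never too low.

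The score is used in four places:
- the primary endpoint (SAP 6.1.9);
- the ANCOVA covariate (SAP 6.1.3);
- the exclusion of baseline scores below 10 from PD analysis set 2 (SAP section 4), on which the primary sensitivity analysis runs (SAP 6.1.4);
- the highest score seen in the trial, which is assigned to every death by Day 15.

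Baseline adjustment need not remove the excess, because it depends on FiO2. A participant with an excess of 2 points at baseline on FiO2 0.5, and a Day 15 FiO2 below 0.5, shows 2 points of improvement that come from the constant alone.

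**Working it through.** **Plan's own figure.** Protocol 12.9.1 assumes 60 per arm, a difference of 3.6, an SD of 9.2 and one-sided alpha of 10%, and states 80% power. Recomputed power is 0.806, with 59 per arm needed for 80%. The stated figure reproduces.

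**Assumptions not in the documents.** Water vapour pressure is 47 mmHg. Barometric pressure follows the standard atmosphere, PB = 760 x (1 - 2.25577e-5 x h)^5.25588, with h in metres.

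**Size of the overstatement.** The constant should be PB - 47. The overstatement is FiO2 x (713 - (PB - 47)).

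| Altitude | PB | PB - 47 | Overstatement at FiO2 0.5 | at FiO2 1.0 |
|---|---|---|---|---|
| 2500 m | 560 | 513 | 100 mmHg | 200 mmHg |
| 3000 m | 526 | 479 | 117 mmHg | 234 mmHg |
| 3600 m | 487 | 440 | 137 mmHg | 273 mmHg |

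The two interior scoring bands are 150 mmHg wide.

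**Worked case, 2500 m, PaCO2 35, PaO2 60.** PaCO2/0.8 = 43.75.

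| FiO2 | A-aDO2 with 713 | Points | A-aDO2 with 513 | Points | Excess |
|---|---|---|---|---|---|
| 0.5 | 253 | 2 | 153 | 0 | 2 |
| 0.6 | 324 | 2 | 204 | 2 | 0 |
| 0.8 | 467 | 3 | 307 | 2 | 1 |
| 1.0 | 609 | 4 | 409 | 3 | 1 |

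**Grid.** FiO2 0.5-1.0, PaO2 50-110 and PaCO2 30-45, all combinations weighted equally:
- 2500 m: 94% are at least 1 point too high, mean 1.3, range 0-2.
- 3000 m: 99% or more, mean 1.6, range 0-3. Three points are possible because at FiO2 0.7 the shift is 0.7 x 234 = 164 mmHg, enough to cross a whole band.
- No combination is scored too low.

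For FiO2 below 0.5, 713 is not used and the excess is exactly 0.

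**Trial level (illustration with assumed shares).** Suppose 5-30% of participants are at such sites, 25-50% of those have FiO2 of at least 0.5 at the endpoint, and the excess is 1-2 points.
- The mean rises by between 0.05 x 0.25 x 1 = 0.01 and 0.30 x 0.50 x 2 = 0.30 points in each arm.
- The SD becomes at most sqrt(9.2^2 + 2^2 x 0.15 x 0.85) = 9.23.
- Power is 0.804-0.806.

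**Table 10-1.** At SpO2 99% the table gives 145 mmHg, already in the 0-point PaO2 band (above 70). At 80% it gives 44 mmHg, already in the 4-point band (below 55). For FiO2 below 0.5 the missing ends are therefore determined. As written, 100% without a blood gas has no PaO2. SAP 6.1.7 then carries a value forward for up to 4 days; without one the item, and with it the total, is missing. For FiO2 of 0.5 or more the missing value can matter: at FiO2 0.6 and PaCO2 40, PaO2 145 gives 233 (2 points), 175 gives 203 (2 points) and 180 gives 198 (0 points).

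**The case against.** The strongest reply is that the effect on the trial is small or unknown. The altitude clause is a contingency; neither document says that such a site was opened or how many participants it would enrol. The constant applies only at FiO2 of 0.5 or more. Participants discharged before Day 15 are scored at discharge, where such an FiO2 is presumably uncommon, and deaths do not use their own A-aDO2. Both arms follow the same rule, so randomisation protects the null comparison. PD analysis set 2 supports a sensitivity analysis only, and the death score changes only if the trial's highest score comes from a high-altitude participant on FiO2 of at least 0.5. The SAP also says it follows a published scoring table, and whether that source corrects for altitude cannot be checked here.

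All of this stands as a limit on size. It does not explain why the protocol lists altitude for the score and the derivation ignores it.

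A reader might infer that every primary score at a high-altitude site is 1-2 points too high, or that 94% of participants there are mis-scored. The documents support neither. Scores with FiO2 below 0.5 are untouched, the excess can be 0 above it (the FiO2 0.6 case), and the 94% is a share of equally weighted grid points, not of participants.

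The Table 10-1 gap is a separate and narrow matter. The worst value in 24 hours is recorded (Protocol 8.3.2), so 100% on high FiO2 without a blood gas should be rare.

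**Conclusion.** The inconsistency is real and should be corrected, but it does not threaten the primary test. For FiO2 of 0.5 or more, the fixed 713 overstates A-aDO2 at 2500 m by about 200 x FiO2 mmHg and raises the oxygenation item by 0-2 points, or 0-3 at 3000 m and above, usually 1-2. These sizes rest on the standard-atmosphere assumption and on the range of blood gases examined.

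Under the assumed shares, the shift is at most 0.30 points per arm against a planned difference of 3.6, and power is essentially unchanged. What remains is avoidable error in individual primary scores and the baseline covariate, in who falls below 10 for PD analysis set 2, and possibly in the value given to every death. If sites use the same formula at screening, it also touches the entry criterion, "Acute Physiologic Assessment and Chronic Health Evaluation (APACHE) II score of ≥ 10 at time of screening"; the documents do not say whether they do.

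**What to change.** In SAP 10.2, item 5, replace 713 with (site barometric pressure - 47). Derive pressure from the recorded site altitude by a standard-atmosphere formula written into the SAP. Use the corrected score wherever APACHE II enters: endpoint, covariate, PD analysis set 2 and death imputation. Report the primary model with the fixed-713 score as a sensitivity analysis.

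As a separate minor change, add end rules to Table 10-1 for FiO2 below 0.5 without a blood gas: SpO2 100% scores in the above-70 mmHg band (0 points) and SpO2 below 80% in the below-55 mmHg band (4 points), instead of carrying an older value forward. For FiO2 of 0.5 or more the SAP would have to state a PaO2 for these readings; the documents give no basis for choosing one.

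The cost is one formula, two scoring rules and one extra model run, made by SAP amendment before database lock. No new data are needed if altitude is recorded as Table 16-3 foresees.
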